**Protocol**

# Post-op Telehealth Mindfulness Protocol for Spinal Surgery

## Design Synopsis

**Title:** Optimizing a Postoperative Telehealth Mindfulness Intervention to Improve Pain-related Outcomes and Reduce Opioid Use After Spine Surgery

**Principal Investigator:** [name]

**Participating Center:** Vanderbilt University Medical Center

**Sponsors:** Osher Center for Integrative Medicine at Vanderbilt (7/1/20 - 6/30/21); NIH - National Center for Complementary and Integrative Health (8/5/21 - 7/31/26)

**Type of study:** Two-arm intervention development and feasibility pilot trial

**Objective:** The overall objectives of our preliminary, mixed-methods project are to optimize a mindfulness-based intervention (MBI) for patients recovering from lumbar spine surgery to improve pain-related outcomes and reduce post-surgical opioid use, and to evaluate its feasibility and acceptability. We will pilot an existing, group-based MBI for chronic pain patients that we have formatted for both one-on-one and group telehealth delivery to postsurgical patients, and utilize participant feedback to tailor the intervention to post-surgical orthopaedic patients.

**Specific Aim 1: To evaluate the feasibility and acceptability of the telehealth MBI.** We will conduct a nonrandomized, sequential pilot test of the individual telehealth MBI (approximately 16 completers) and of the group telehealth MBI (approximately 8 completers) with patients recovering from lumbar spine surgery. We anticipate enrolling up to 34 participants to have 24 complete the study. Feasibility and acceptability of the individual and group intervention will be evaluated as recruitment rates, session attendance, home practice assignment, study retention, and participant satisfaction.

**Hypothesis 1:** a) Participants will be recruited at a rate of 50%; b) Participants will attend 90% of sessions on average; c) Participants will complete 80% of home practice assigned; d) Study retention will be 90% at post-intervention; e) 80% of participants will report moderate to high satisfaction with the intervention.

**Specific Aim 2:** To further tailor the telehealth MBI to post-surgical orthopaedic patients. Using structured qualitative interviews and a post-intervention satisfaction survey during the open-label pilot test, we will obtain participant feedback regarding the one-on-one telehealth format, intervention components, and relevance to post-surgical concerns. Qualitative interviews will be coded and analyzed to inform revisions to the intervention.

**Expected outcome:** The intervention will be revised based on participant feedback.

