## Post-op Telehealth Mindfulness Protocol for Spinal Surgery

**Study design:** Two-arm, nonrandomized mixed-methods behavioral intervention trial

**Study duration:** 1 year (1-month start-up; 7 months accrual; 2 additional months for intervention completion and data collection; 2 months for data analysis and intervention adaptation)

**Sample size:** Up to 34 eligible patients will be consented; Approximately 16 patients will complete the individual intervention; 8 patients will complete the group intervention (consented and completion sample size may vary depending on when data saturation from qualitative interviews is reached).

**Number of study sites:** 1

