**Outcome measures:**

***Primary outcomes:***

Intervention feasibility and acceptability (enrollment, session attendance, homework completion, intervention retention, intervention satisfaction, semi-structured interview).

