## **5. Trial Protocol**

**5.1. Overview.** The patient-related activities of the postoperative telehealth mindfulness trial can be divided into the following phases.

- Phase 1: Consent into study and screening for eligibility
- Phase 2: Enrollment into trial prior to surgery, preoperative data collection
- Phase 3: Postoperative Baseline data collection (2 weeks after surgery)
- Phase 4: Intervention (8 weeks)
- Phase 5: Post-intervention data collection and semi-structured interviews (3 months after surgery)

**5.2. Phase 1: Consent into Study and Screening for Eligibility.** Patients will be approached for their consent to participate in the study following their preoperative clinic visit either at the clinic as available or over the phone, with the permission of the treating surgeon. If over the phone, participants will sign an e-consent form through a REDCap survey link. The study coordinator will perform the consent process using a scripted dialogue and materials developed for the study.

Patients will then be screened for eligibility in the surgical center or over the phone by the research coordinator. Screening through the medical record will occur prior to surgery and a scheduled preoperative clinic visit. Additional screening will occur either immediately after the preoperative clinic visit at the Spine Center or after the visit over the phone by the study coordinator through a list of screening questions. All potentially eligible patients will be entered into REDCap, a study number assigned, and eligibility criteria confirmed.

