## 6. Statistical Analyses.

**6.1. Statistical Analysis Plan.** Descriptive statistics will be used to summarize quantitative feasibility outcomes with numbers and rates. Benchmarks for success of the telehealth MBI will be: 1) enrollment rate of at least 50% of eligible patients; 2) 90% of sessions attended on average; 3) 80% of home practice completed on average; 4) intervention retention of at least 90%; 5) moderate to high intervention satisfaction rated by at least 80% of participants.

Transcription of interview data will be verified prior to analysis. The PI and study personnel will conduct line by line analysis using Dedoose analytic software. Themes and textual examples will be independently identified and subsequently discussed for consensus. Analysis will be an ongoing, iterative process following each 2 to 4 interviews to ensure that data saturation ultimately occurs before discontinuing interviews. A codebook will be generated by isolating individual quotes and refined as additional interviews are coded. Thematic analysis of codes will be used to identify emergent themes, or patterns of meaning, found in the data with regards to participant experiences with the telehealth MBI and specific post-surgical concerns. Quantitative and qualitative data results will be merged to identify aspects of the telehealth MBI that need to be adapted to optimize acceptability for post-surgical patients.

Within-group, within-subject changes from baseline to the follow-up post-intervention assessment in pain-related outcomes, opioid use, and psychosocial characteristics will be explored by examining change in scores and their respective standard errors with 95% confidence intervals.

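### Does the 90% retention benchmark need redefining because it carries two names and no stated denominator?

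*Combined protocol and SAP*

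**What the plan says.** Specific Aim 1 in the Design Synopsis lists the feasibility measures as "recruitment rates, session attendance, home practice assignment, study retention, and participant satisfaction", and Hypothesis 1d sets the target: "Study retention will be 90% at post-intervention". The primary outcome, in the synopsis and again in section 5.7, is worded differently: "enrollment, session attendance, homework completion, intervention retention, intervention satisfaction, semi-structured interview". Section 6.1 follows that second wording and sets "intervention retention of at least 90" per cent as the fourth of five benchmarks.

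On numbers, Aim 1 states: "We anticipate enrolling up to 34 participants to have 24 complete the study". The Sample size entry of the synopsis splits the completers by format: "Approximately 16 patients will complete the individual intervention; 8 patients will complete the group intervention". It adds that the "consented and completion sample size may vary depending on when data saturation from qualitative interviews is reached".

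On sequence, sections 5.1 to 5.6 put consent first. Section 5.2 then continues: "Patients will then be screened for eligibility". Pre-operative data collection, surgery, the 2-week baseline, the sessions and the 3-month assessment follow. Section 5.9, headed Retention, pays separately for each of the three assessment surveys and for the interview. It links no payment to session attendance.

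**The concern.** Study retention usually means staying in follow-up, and intervention retention means staying in treatment. A single 90% attached to both names, without a numerator or denominator, could be worked out in several ways. The denominator matters in this design because participants can be lost between pre-operative enrolment and session 1. Such losses lower a rate taken over everyone enrolled but leave a rate among starters untouched. The enrolment benchmark in the same sentence of section 6.1 does name its denominator (eligible patients), so the omission for retention stands out.

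The sample size seems to add to the difficulty. Going from 34 enrolled to 24 completers allows for far more loss than 10%, and no basis is given. Feasibility is the primary outcome. If the same participants could be reported as a pass or a miss, depending on a choice made after the data are seen, one of the five benchmarks would tell readers little.

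**Working it through.** **One benchmark or two.** The two lists, side by side:

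| Position | Hypothesis 1 | Section 6.1 |
|---|---|---|
| 1 | recruitment, 50% | enrolment, at least 50% |
| 2 | session attendance, 90% | session attendance, 90% |
| 3 | home practice, 80% | home practice, 80% |
| 4 | study retention, 90% | intervention retention, at least 90% |
| 5 | satisfaction, 80% | satisfaction, at least 80% |

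The order and percentages match throughout. Other labels drift too: recruitment becomes enrolment, and home practice becomes homework in the outcome lists. Every participant is offered the intervention and there is no untreated arm. The change of name in row 4 fits the same loose drafting.

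**Numerator.** Hypothesis 1d fixes the time at post-intervention. Sections 3.1 and 5.1 equate that with the assessment 3 months after surgery. The timetable agrees: a participant who starts straight after the 2-week baseline and uses the full 10 weeks allowed finishes at 2 + 10 = 12 weeks. The natural numerator is therefore participants assessed at 3 months.

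**Does 34 contradict 90%?** Inputs from the synopsis: ceiling 34, completers 16 + 8 = 24, retention 0.90.

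- Completers over the ceiling: 24/34 = 70.6%. Implied loss: 10/34 = 29.4%.
- Enrolment needed at 90% overall: 24/0.90 = 26.7, rounded up to 27. The plan's 34 is not reproduced; it is 7 higher.
- 90% among starters only: 24/0.90 = 26.7 starters, so loss before session 1 of 1 − 26.7/34 = about 22%. Losses at screening after consent, at surgery or at the baseline survey could supply this. The documents give no rate for any of them.
- 34 enrolled at 90% retained: 0.90 × 34 = 30.6. Then 31/34 = 91.2% meets the benchmark and 30/34 = 88.2% misses it.

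The shortfall at 34 appears only if the numerator is held at 24 while enrolment rises to its ceiling. The plan gives 24 as a target and 34 as an upper limit, and lets both vary.

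**How much the denominator can matter.** With 24 in the numerator:

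| Denominator | Rate | Exact 95% CI |
|---|---|---|
| 34 | 70.6% | 53% to 85% |
| 27 | 88.9% | 71% to 98% |
| 26 | 92.3% | 75% to 99% |

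The spread from 26 to 34 is 92.3 − 70.6 = 21.7 percentage points. One participant, 26 against 27, moves the result across 90%, and both of those intervals extend well to either side of it. A pass or miss at this sample size carries little information without the count beside it.

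**The case for a change.** The strongest case for a change is that these benchmarks are the trial's main quantitative result, and that section 6.1 presents them as criteria of success. The sponsor named a denominator for enrolment and could have done so for retention. On the planning figures, an all-enrolled rate misses by 90 − 70.6 = 19.4 points, while a rate among 26 starters passes, so the choice could be made once the answer is known. Section 5.6 also sends the 3-month survey after the intervention is completed, without saying whether people who stop attending receive it.

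Part of this stands. The denominator is unstated, the name changes, and the plan does not promise counts at each stage. But section 6.1 undertakes to report numbers as well as rates, so readers should see which denominator was used. Enrolment and attendance are separate benchmarks and help to show where losses fall. Section 5.6 gives the survey a calendar time, and section 5.9 pays for it whatever the attendance. Neither settles the follow-up of those who stop, but both fit surveying everyone. Writing in a definition would still leave the sponsor to choose which rate carries the 90%. The choice would be clearer, but no result that the plan now yields would be corrected.

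**Conclusion.** The observation about wording is accurate, but it does not call for a change to the plan. The likelier reading is a single benchmark, loosely named, with its numerator anchored to the 3-month assessment. The step from 34 to 24 is an unexplained margin above 27, and it is consistent with a ceiling set before screening, surgery and baseline. It contradicts no stated figure.

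The one real gap is the denominator. At the extremes illustrated it is worth 21.7 percentage points (70.6% against 92.3%), with 24 completers held fixed. It does not affect an error rate or a sample size calculation, and no rule ties further action to the 90%.

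This conclusion assumes that the analysts report the retention count with its denominator, as the promise of numbers and rates implies, and that they show losses before session 1 in an ordinary account of participant flow. On that footing, following the plan as written would not give a wrong result.

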## Post-op Telehealth Mindfulness Protocol for Spinal Surgery

**Study design:** Two-arm, nonrandomized mixed-methods behavioral intervention trial

**Study duration:** 1 year (1-month start-up; 7 months accrual; 2 additional months for intervention completion and data collection; 2 months for data analysis and intervention adaptation)

**Sample size:** Up to 34 eligible patients will be consented; Approximately 16 patients will complete the individual intervention; 8 patients will complete the group intervention (consented and completion sample size may vary depending on when data saturation from qualitative interviews is reached).

**Number of study sites:** 1

**Inclusion criteria:**

- 1) English-speaking adults
- 2) Between the ages of 18 and 90
- 3) Scheduled for a laminectomy and/or fusion
- 4) scheduled for their first lumbar spine surgery
- 5) Radiographic evidence of a degenerative condition including but not limited to *spinal stenosis, spondylosis with or without myelopathy, and spondylolisthesis*
- 6) Presence of back and/or lower extremity pain persisting for at least 3 months
- 7) Access to stable internet.
- 8) Able to participate in weekly, remote sessions with a study therapist for 8 weeks after surgery

**Exclusion criteria:**

- 1) Microsurgical technique as the primary procedure (i.e. isolated laminotomy or microdiscectomy)
- 2) Having surgery for the primary indication of a spinal deformity
- 3) Having surgery secondary to pseudarthrosis, trauma, infection, or tumor
- 4) Current/history of a primary psychotic or major thought disorder or hospitalization for reasons related to psychosis
- 5) Diagnosis of Alzheimer's disease or another form of dementia
- 6) Traumatic Brain Injury (greater than mild severity)
- 7) History of bipolar disorder or dissociative disorder
- 8) Schizophrenia or other psychotic disorder (e.g. brief psychotic disorder, delusional disorder)
- 9) Active substance use disorder (in past month)
- 10) Current Posttraumatic Stress Disorder (PTSD) symptoms (in past month)

**Outcome measures:**

***Primary outcomes:***

Intervention feasibility and acceptability (enrollment, session attendance, homework completion, intervention retention, intervention satisfaction, semi-structured interview).

***Secondary Outcomes:***

- 1) PROMIS-29 – Pain Intensity and Pain Interference

Detailed Protocol

Version 7; November 22, 2021

## Post-op Telehealth Mindfulness Protocol for Spinal Surgery

- 2) Pain bothersomeness (1 item)
- 3) Oswestry Disability Index (ODI)
- 4) Self-reported and EMR-collected opioid dosage
- 5) PROMIS-29 – Depression scale
- 6) PROMIS-29 – Anxiety scale
- 7) Pain Self-efficacy questionnaire (PSEQ)
- 8) Five-Facet Mindfulness Questionnaire-15 (FFMQ-15)
- 9) Perceived Stress Scale – 4
- 10) Pain Catastrophizing Scale
- 11) Tampa Scale for Kinesiophobia - 13

**Statistical analysis:** *Primary outcomes:* Descriptive statistics to summarize feasibility and acceptability outcomes with numbers and rates. Qualitative interview analysis of transcribed interviews using line by line analysis and identification of themes and textual examples. Quantitative and qualitative data results will be merged to identify aspects of the telehealth MBI that need to be adapted to optimize acceptability for post-surgical patients. *Secondary outcomes:* Within-group, within-subject changes from baseline to the follow-up post-intervention assessment in pain-related outcomes, opioid use, and psychosocial characteristics will be explored by examining change in scores and their respective standard errors with 95% confidence intervals

**Safety monitoring:** The PI and research coordinator will monitor the accumulated data as the trial progresses to ensure patient safety, evaluate recruitment, and assess overall data quality.

## 1. Primary Hypothesis and Principal Objective

Lumbar spine pain is the leading cause of years lived with a disability and affects over 50 million individuals in the United States. As the population over age 60 grows, rates of spine surgeries performed to address degenerative spine conditions have increased markedly. Yet, more than 40% of patients experience poor pain, functional, or quality of life outcomes after surgery. Moreover, despite the limited efficacy and high risks associated with long-term prescription opioid use, up to 50% of patients are prescribed opioids 12 months following lumbar spine surgery. Pre- and post-surgical psychosocial factors are robust determinants of long-term post-surgical outcomes and continued opioid use.

Psychosocially informed interventions are recommended after spine surgery but not standard practice. Patients recovering from spine surgery identify a need for nonpharmacological strategies to decrease pain and emotional distress. Mindfulness-based interventions (MBIs) demonstrate efficacy for improving chronic pain outcomes, reducing opioid use or desire, and favorably impacting pain sensitivity and psychosocial risk factors for persistent pain and disability. To date, **no studies have** tested the usefulness of an MBI in patients following spine surgery to manage post-surgical pain and reduce long-term opioid use. The group-based, in-person delivery format renders the typical MBI highly impractical for post-surgical patients who live several hours away from the surgical centers of excellence. Prior work indicates that telehealth MBIs (via live, online video) are feasible in chronic pain populations and are a promising alternative.

The overall objectives of our preliminary, mixed-methods project are to tailor an MBI for patients recovering from spine surgery and to evaluate its feasibility and acceptability. We will pilot an existing, group-based MBI for chronic pain patients that the principal investigator (PI) modified for both one-on-one and group telehealth delivery for postsurgical patients, and utilize participant feedback to tailor the intervention to post-surgical orthopaedic patients. The purpose of the intervention is to improve pain-related outcomes and reduce post-surgical opioid use, so outcome measures will be collected to evaluate feasibility of data-collection procedures and pre-post changes.

## 2. Background and Significance

**Lumbar spine surgery outcomes are poor for up to 40% of patients.** Spine pain affects millions of individuals in the United States and results in poor quality of life, reduced mental and physical functioning, and billions of dollars in healthcare costs and lost productivity. Complete resolution of chronic spine pain is uncommon. Lumbar spine surgery is the most common elected surgery to treat degenerative spinal conditions when conservative treatments are unsuccessful. As the population of older adults grows, rates of lumbar spine surgery have increased markedly. However, up to 40% of patients experience continued or worsening pain and disability following surgery. Studies find that patients' expectations for improvement after surgery exceed their experienced reductions in back pain and leg pain, and improvements in functioning. A substantial number of patients who experience a significant reduction in pain intensity after spine surgery nonetheless report continued pain interference and disability, suggesting that multiple factors and not merely a reduction in pain intensity, contribute to improved functional outcomes.

**Prolonged prescription opioid use is common following spine surgery.** Studies indicate that 59% to 65% of patients taking opioids pre-operatively continue to receive opioids 12 months following spine surgery. Furthermore, as many as 26% of patients who were opioid-free prior to spine surgery do not achieve opioid independence 12 months after surgery. These findings are concerning, given the numerous risks of prolonged opioid use, including tolerance, opioid-induced hyperalgesia (paradoxically increased pain sensitivity), misuse, abuse, and overdose, all of which can complicate post-surgical recovery. Effective strategies are needed to help patients reduce unnecessary or prolonged opioid use following surgery.

**Psychosocial factors are key predictors of post-surgical outcomes and opioid use.** It is widely recognized that pain is experienced through a complex interaction of physical/neural, cognitive, affective, behavioral, and social factors. Studies consistently indicate that both pre and post-surgical psychosocial factors are robust predictors of surgical outcomes. Pre- and early post-surgical psychological distress, particularly depression and anxiety, significantly predict worse pain intensity and disability, physical functioning, and quality of life, as well as prolonged opioid use at 6 to 12 months following lumbar spine surgery. Individual coping style and cognitive factors, such as passive avoidant coping, high fear avoidance beliefs, and pain catastrophizing are associated with worse spine surgery outcomes. Conversely, higher levels of self-efficacy and positive affect are protective and associated with more favorable outcomes after orthopaedic surgery.

Psychosocially informed interventions are recommended after surgery, but are not standard practice, despite promising research. Patients indicate a need for nonpharmacologic strategies to cope with post-surgical pain and emotional distress and as alternatives to taking pain medication. Randomized controlled trials demonstrate that biopsychosocial rehabilitation programs targeting cognitive and behavioral factors after lumbar spine surgery result in improved pain, mental and physical functioning, pain self-efficacy, fear of movement, and pain coping compared with exercise or education alone. The majority of trials draw from traditional cognitive behavioral therapy for chronic pain. Although effective at improving pain-related outcomes, not all patients achieve benefit from cognitive behavioral therapy. Alternative biopsychosocial approaches to postoperative rehabilitation and pain management are needed in order to provide more widely effective and personalized treatment. The

